Study Protocol

Title: Informing Treatment Decisions in the Central Disorders of Hypersomnolence: A Pragmatic Clinical Trial of Modafinil Versus Amphetamines

NCT Number: NCT03772314

Protocol date: September 25, 2020

TITLE: Informing Treatment Decisions in the Central Disorders of Hypersomnolence: A Clinical Trial of Modafinil Versus Amphetamines

Short Title: A Clinical Trial of Modafinil Versus Amphetamines

PI: [name] [name], MSc, Associate Professor of Neurology

Funder: American Association of Sleep Medicine Foundation

Protocol Version: 8.0

Protocol Date: 9/25/2020

Abstract

Currently, there are insufficient data to guide clinical practice regarding the use of amphetamines for the treatment of narcolepsy. This may be particularly important in the case of narcolepsy type 2, for which randomized, controlled trial data show that other treatments are less beneficial than they are for participants with narcolepsy type 1. For the closely related disorder of idiopathic hypersomnia, clinical trial data to guide treatment decision-making are even more limited, with only three published controlled trials ever performed.

To address these evidence gaps, we propose a randomized, active-treatment controlled trial comparing modafinil and amphetamine salts for the treatment of narcolepsy type 2 and idiopathic hypersomnia. The primary outcome will be reduction in excessive daytime sleepiness, as measured by change in Epworth Sleepiness Scale scores from baseline to week 12 on treatment. Other important patient-reported outcomes will be considered as secondary outcomes, including Patient Global Impression of Change for sleep inertia, cognitive dysfunction, and sleepiness.

In addition to directly comparing the efficacy of these two medications for hypersomnolent patients, this study will also evaluate for relatively safety in this population. Further, we will assess for clinical predictors of treatment response. All three of these aims will be complementary in informing shared decision-making about whether to treat with modafinil or amphetamine salts.

Background

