Aim 1: To compare the effectiveness of modafinil and amphetamine salts in patients with narcolepsy type 2 or idiopathic hypersomnia. The primary outcome will be the change in Epworth Sleepiness Scale score from pre-treatment baseline. Secondary outcomes will include Patient Global Impression of Change from baseline for sleepiness, sleep inertia, and cognitive dysfunction.

Aim 2: To compare the safety of modafinil and amphetamine salts in the treatment of narcolepsy type 2 or idiopathic hypersomnia.

Aim 3: To evaluate for clinical predictors of response to modafinil and amphetamine salts in these patients.

Study Design & Methods

Treatment-naïve adult patients (n = 44), or adult patients free of wake-promoting medication or willing to discontinue current wake-promoting medication seeking evaluation at the Emory Sleep Center for narcolepsy type 2 or idiopathic hypersomnia will be invited to participate and randomized to one of the treatment arms upon consent. Although pragmatic trials often do not involve blinding to condition, those trials where outcomes of interest are primarily subjective often require blinding to minimize bias (20), which will be necessary in this case. Randomization, allocation concealment, blinding, and medication dispensing will be managed by Emory's Investigational Drug Service (IDS). The IDS will use 1:1 computer generated randomization (23), with a block design to ensure equal number of participants receiving each study medication. Block size will not be disclosed to the study investigators or staff. Identity of medications will be concealed by the pharmacy using matched pills and pill containers. The IDS is located in a separate building from the study team and will have no interaction with participants. Medications will be transferred from the pharmacy via courier. This protocol will be approved by the Emory University Institutional Review Board and registered at clinicaltrials.gov prior to enrollment of the first participant.

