- 3) Inclusion criteria will be changed to eliminate the need for PSG/MSLT. The Emory sleep lab is currently closed for non-urgent procedures, and so no patients suspected of having idiopathic hypersomnia or narcolepsy can currently undergo PSG/MSLT. We will use the following for the provisional diagnosis of idiopathic hypersomnia or narcolepsy type 2 during the period that the sleep lab is closed for testing:
 - a. Clinical suspicion of idiopathic hypersomnia or narcolepsy type 2 by a sleep medicine provider
 - b. Home sleep apnea test demonstrating absence of obstructive sleep apnea (pAHI < 15), if sleep medicine provider feels that a home sleep apnea test is clinically indicated to rule out sleep apnea
 - c. Sleep diary x 1 week demonstrating average sleep time > 7 hours/night and no individual nights of < 6 hours
 - d. Other inclusion/exclusion criteria will continue to apply

Exclusion criteria will include obstructive sleep apnea (AHI > 15), severe periodic limb movements of sleep with arousals (PLM arousal index > 30), allergy to either of the study drugs, and contraindication to either of the study drugs. For modafinil, these contraindications include: history of left ventricular hypertrophy, mitral valve prolapse, severe cardiovascular disease, unstable angina, myocardial infarction, severe hepatic impairment, substance abuse history, psychosis, or unstable depression or mania (25). Contraindications to amphetamine salts, in addition to those listed above, include: other cardiac structural abnormalities, cardiomyopathy, severe arrhythmias, uncontrolled hypertension, glaucoma, Tourette's syndrome, and epilepsy. Women who are pregnant, planning to become pregnant within 16 weeks, or breastfeeding will be excluded, as the safety of these medications during pregnancy and breastfeeding is not well-established. Participants who have taken either modafinil or amphetamine salts for another indication (e.g., ADHD) will be excluded if it has been < 12 months since this treatment.

Participants who are taking a medication that has a potential interaction with modafinil to cause QTc prolongation will be eligible if either: 1) they can safely discontinue the potentially interacting medication prior to and throughout the study (in conversation with the prescribing physician), or 2) they undergo an an electrocardiogram (EKG) prior to baseline visits that shows a normal QTc interval while on the potentially interacting medication.

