APPENDIX 1. SCHEDULE OF STUDY VISITS

	VISIT 1	VISIT 2 – SLEEP STUDY	VISIT 3	VISIT 4	VISIT 5
Informed Consent	X				
Medical History	X				
Study Inclusion/Exclusion	X				
Concomitant Medication Review	X	X	X	X	X
Wean off current wake- promoting medicines	X				
Adverse Experiences		X	X	X	X
Participant Payment	X				X
PSG/MSLT sleep study		X			
Sleepy Packet	X				
Sleep Inertia Questionnaire	X	X	X	X	X
Epworth Severity Scale	X	X	X	X	X
CGI- Baseline Questionnaire	X	X	X	X	X
CGI- Sleep Inertia Questionnaire	X	X	X	X	X
CGI- Sleepiness Questionnaire	X	X	X	X	X
CGI- Cognitive Dysfunction Questionnaire	X	X	X	X	X
Treatment Questionnaire	X	-	X	X	X
Treatment Comparison Questionnaire	X	-	X	X	X
Study Drug Titration Reviewed	X				
Randomization	X	OR X			
Dispensing or Administration of Study Drug	X	OR X	X	X	
Counting of Returned Study Drug			X	X	X

Informed Consent Process

Consent will be obtained in-person from a study PI, co-I, or coordinator. Comprehension will be ensured by allowing ample time for questions and discussion and verbally reviewing the information with the subject in addition to reviewing the written consent form. The discussion will take place at the Emory Sleep Center.

Compensation

Participants will be compensated \$25 for visit 1 (enrollment) and \$25.00 for the week 12 study visit (visit 5), for a total of \$50.

Statistical Analysis

Sample size will be 22 in each group. This sample size is sufficient to demonstrate a reduction in ESS of 4 points with amphetamine salts, assuming a standard deviation of change from baseline of 6.2 (35). This is

a conservative, but clinically significant, change in Epworth, compared to the observed change from baseline of 5.3 points in clinical trials of modafinil [weighted average from (15, 35, 36)]. This sample size provides 82.8% power to find a moderately large effect size for amphetamine salts. For non-inferiority, we will use a responder definition of those achieving a 25% reduction in ESS, a data-driven minimal clinically significant change in patients with narcolepsy (29). Assuming 80% of participants meet this threshold, 22 participants per group will provide 80% power to a non-inferiority limit of 30% (37, 38).

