Intention-to-treat analyses will be performed, using last observation carried forward in the event of participant drop-out. The change in ESS at week 12 from baseline will be compared between the two treatment groups via t-test (compared for unequal variances if necessary) and will be evaluated on a hypothesis of non-inferiority. Similar analyses will be performed on secondary outcomes, considering the proportion of responders in each treatment arm who rate themselves "much improved" or "very much improved". Categorical outcomes, including these PGI-C proportions and adverse events, will be compared using Chisquare or Fisher exact test. Exploratory analyses will evaluate response at week 4 and week 8 between the two medications groups, to determine if there is a difference in time to symptom control.

Considering each medication separately, predictors of response will be assessed using logistic regression. The main predictor of interest will be hypersomnia diagnosis, i.e., narcolepsy type 2 or idiopathic hypersomnia. Other predictors, to be considered in separate, exploratory regression models, include: MSLT mean sleep latency, MSLT number of SOREMs, sex/gender, baseline ESS, age, and comorbidities. Significant predictors in univariate models will be combined in a multivariate model. Although the investigative team has extensive clinical trial and statistical experience, additional statistical consultation will be provided as needed through Emory's CTSA consultation program.

Data Safety Monitoring and Reporting

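### Aim 3 models predictors of response within each drug only; an exploratory pooled treatment-by-predictor contrast with its confidence interval would cheaply serve the stated purpose of choosing between the drugs

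*Combined protocol and SAP*

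**What the plan says.** The Objectives state: "Aim 3: To evaluate for clinical predictors of response to modafinil and amphetamine salts in these patients". The Abstract gives the use to which the results will be put: "All three of these aims will be complementary in informing shared decision-making about whether to treat with modafinil or amphetamine salts".

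The Statistical Analysis section carries out Aim 3 in four steps:
- Separate fits by drug: "Considering each medication separately, predictors of response will be assessed using logistic regression".
- A lead predictor: "The main predictor of interest will be hypersomnia diagnosis, i.e., narcolepsy type 2 or idiopathic hypersomnia".
- Further factors (sleep latency, SOREM count, sex/gender, baseline ESS, age, comorbidities): "Other predictors, to be considered in separate, exploratory regression models". The exploratory label is attached to these models and not to the diagnosis model.
- A significance screen: "Significant predictors in univariate models will be combined in a multivariate model".

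No pooled model, treatment-by-predictor term or comparison of coefficients between arms appears anywhere in the document.

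On diagnosis itself, the pandemic modifications in Study Design & Methods drop the PSG/MSLT requirement and rely on a "provisional diagnosis of idiopathic hypersomnia or narcolepsy type 2 during the period that the sleep lab is closed for testing". The two disorders are named jointly there, while the Background says that only the MSLT tells them apart.

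**The concern.** A clinician choosing between the drugs needs to know whether a patient characteristic shifts response more under one drug than under the other. That is a between-drug contrast, and two separate within-drug models do not report it. What they report is a pair of p-values, and the screen on univariate significance draws attention to them. When a factor acts equally under both drugs and each arm has only 22 patients, it will often reach significance in one arm and miss in the other by chance. That pattern could be read as a reason to prefer one drug.

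The estimate could be recovered later by subtracting the two univariate log odds ratios. This is unplanned, and with unpenalised estimates it has no finite answer when a diagnosis group within an arm has all or no responders.

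**Working it through.** **Plan's own figures.** The plan gives no power or precision for Aim 3. Its stated figures do reproduce. A within-arm t-test with n = 22, a 4-point change, SD 6.2 and two-sided 0.05 gives 82.3% power (plan: 82.8%). For non-inferiority at 80% response and a 30-point margin, 0.30 / √(2 × 0.16 / 22) = 2.49 and Φ(2.49 − 1.645) = 80%, at one-sided 0.05. Neither figure concerns predictors.

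**Inputs.** From the Statistical Analysis section: 22 per arm, SD of change 6.2, and "Assuming 80% of participants meet this threshold". Assumed, because the documents give no diagnosis mix: a per-arm split of 11/11, with 16/6 as the uneven case. Also assumed: response rates by diagnosis of 90% vs 70%, or 70% vs 40%, identical under both drugs.

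**1. Significant in exactly one arm when there is no drug difference.** Let q be the power of one arm's test at two-sided 0.05, by exact enumeration. The chance that exactly one arm is significant is 2q(1 − q).

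| Response by diagnosis (11/11) | Fisher | Wald | Likelihood ratio |
|---|---|---|---|
| 90% vs 70% | q = 0.075, 13.9% | q = 0.035, 6.7% | q = 0.303, 42.3% |
| 70% vs 40% | q = 0.165, 27.5% | q = 0.280, 40.3% | q = 0.319, 43.4% |

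The Wald column counts tables with an infinite odds ratio as not significant. The plan does not say which test the logistic models will use.

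**2. Pooled interaction in the same scenarios.** The penalised (Firth) fit of the saturated model adds 0.5 to each cell. A Wald test of the interaction falsely flags a drug difference in 1.0% of all trials at 90/70 and in 3.7% at 70/40. Among trials with exactly one Fisher-significant arm, the rates are 4.9% and 10.9%. So in about 95% and 89% of the trials that invite the misreading, the interaction test does not support it.

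**3. Whether subtraction after the event is dependable.** With no diagnosis effect and response rate p, the chance of an infinite odds ratio in one arm is s = 1 − [1 − pⁿ¹ − (1 − p)ⁿ¹][1 − pⁿ² − (1 − p)ⁿ²]. For at least one arm it is 1 − (1 − s)². At p = 0.80:
- 11/11: s = 16.4%, giving 30%.
- 16/6: s = 28.3%, giving 49%.

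The problem shrinks at lower response: 3.5% to 15% at p = 0.65, and 0.4% to 6.2% at p = 0.50.

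**4. Precision of the interaction, ESS change, all 44 participants, before baseline adjustment.** SE = 6.2 × √[2(1/a + 1/b)], where a and b are the diagnosis counts per arm; t(40) = 2.02.
- 11/11: SE 3.74, half-width 7.6 points, power for a 4-point interaction 18%.
- 16/6: SE 4.20, half-width 8.5 points, power 15%.

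**5. Precision of the ratio of odds ratios.** The 95% interval multiplies and divides the estimate by exp(1.96 × SE), with SE = √{2[1/(n₁p₁(1 − p₁)) + 1/(n₂p₂(1 − p₂))]}.
- 70/40, 11/11: factor 12.
- 90/70, 11/11: factor 28.
- 90/70, 16 at 90% and 6 at 70%: factor 29.
- 90/70, 6 at 90% and 16 at 70%: factor 58.

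At the 80% planning rate, 44 × 0.20 = 8.8, so about 9 non-responders would inform the logistic version.

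**The case against.** The strongest reply is that nothing is broken. Aim 3 asks for predictors of response to each drug and the within-arm models answer that. The Abstract says only that the aims are complementary in informing decisions, and the plan never says it will compare significance across arms. The misreading would be the reader's. The gain is also modest: an interaction with 15% to 18% power for 4 points settles little. All of this stands, and it is why the point is an improvement rather than a correction.

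Several stronger readings are tempting and are not supported:
- That the plan contradicts Aim 3. It does not; the gap is against the use stated in the Abstract.
- That the between-drug information is lost. The univariate log odds ratios can be subtracted whatever the multivariable models contain.
- That pooling cures infinite odds ratios. An unpenalised interaction model fails in the same tables. Penalisation is the cure, and it could be applied within each arm too.
- That the interaction is wrong in only 1.0% or 3.7% of the misleading trials. Those are rates over all trials; among trials with exactly one Fisher-significant arm they are 4.9% and 10.9%.
- That untested entrants undermine the diagnosis model. Their number is not given and may be zero, and a provider's suspicion may name one disorder. The Background also says that tested patients often change category on repeat testing, so testing does not guarantee correct grouping.

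**Conclusion.** The point holds as a low-cost improvement that should be made. The plan meets Aim 3 as worded, but it specifies no estimate of whether diagnosis or any other factor predicts response to one drug rather than the other. With an equal diagnosis effect under both drugs, exactly one arm would be significant by Fisher test in 14% to 28% of trials, and in 7% to 43% across the three tests examined. These rates rest on the assumed 11/11 split and response rates.

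The added contrast brings an honest interval, not power. Its absence of significance must not be read as equal effects under the two drugs. The coding of pandemic entrants is a secondary gap in detail. The primary ESS comparison is not touched.

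**What to change.** Amend the SAP before unblinding:
1. Keep the within-arm effects. For each predictor, add one pooled model with treatment, predictor and their interaction, plus baseline ESS unless that is the predictor.
2. Use continuous week-12 ESS as the main outcome. As supportive, use logistic regression for a named responder outcome, penalised for sparse cells. The section mentions both a 25% ESS reduction and PGI-C improvement without saying which one the predictor models use.
3. Report each interaction with its 95% CI beside the within-arm effects. Label all of it exploratory, including diagnosis. State that significance in one arm only is not evidence of a drug difference.
4. Before unblinding, code any entrants without PSG/MSLT as a separate category or by their recorded provisional diagnosis. Add a sensitivity analysis limited to tested participants, and report the number untested per arm.

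**Cost.** Wording only; no new patients, visits or data. The downsides should be stated openly:
- The interactions are imprecise: about 7.6 to 8.5 ESS points either way, and roughly 12- to 58-fold either way on the ratio of odds ratios.
- There is one interaction for each of at least seven predictors, without multiplicity control.
- The logistic version has few non-responders.
- The adjusted or penalised fits will not exactly match the planned within-arm odds ratios.
- The tested-only analysis may be smaller, by a number the documents do not give.

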This study will recruit up to 55 participants, with a sample size target of 44 participants who complete participation in the 12 week medication trial. Participants will be newly diagnosed, medication-naïve individuals, or formerly diagnosed, free of wake-promoting medication or willing to discontinue current wake-promoting medication with diagnoses of: narcolepsy type 2 or idiopathic hypersomnia.

Inclusion criteria will be: 1) narcolepsy type 2 or idiopathic hypersomnia; 2) age 18-65; 3) informed consent.

Exclusion criteria will be: 1) contraindication to modafinil or amphetamine salts (history of left ventricular hypertrophy, mitral valve prolapse, other cardiac structural abnormalities, severe cardiovascular disease, unstable angina, myocardial infarction, cardiomyopathy, severe arrhythmias, uncontrolled hypertension, severe hepatic impairment, substance abuse history, psychosis, glaucoma, Tourette's syndrome, and epilepsy); 2) obstructive sleep apnea (AHI > 15); 3) severe periodic limb movements of sleep with arousals (PLM arousal index > 30); 4) allergy to either of the study drugs; and 4) pregnancy or breastfeeding.

Participants who withdraw from study medication will be invited to complete remaining questionnaires/study visits.

Visit Schedule

Visit 1: Enrollment: After reviewing information about the study and confirming participation, subjects will answer questions about their sleep disorder and the symptoms experienced. This visit is expected to last about one hour. If participants are suspected of having a diagnosis of narcolepsy type 2 or idiopathic hypersomnia and have never had an overnight polysomnogram (PSG) and next-day MSLT, they will be scheduled for an

additional study visit to complete a PSG and MSLT before visit 3. If participants already have a confirmed diagnosis of narcolepsy type 2 or idiopathic hypersomnia and are taking certain stimulant medications they will be asked to wean off of this medication before and during the study. After weaning off of medicines, the participant will be given a four-week supply of one of the two study medications. The medication will be provided will be assigned randomly, the participant and the doctor will not be told which of the two study medications are given.

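### Aim 3 models an undefined yes/no response by logistic regression in arms of 22; continuous ESS change, already collected, is always estimable and has more power, though still little

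*Combined protocol and SAP*

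**What the plan says.** The Statistical Analysis section gives Aim 3 its method: "Considering each medication separately, predictors of response will be assessed using logistic regression". It continues: "The main predictor of interest will be hypersomnia diagnosis, i.e., narcolepsy type 2 or idiopathic hypersomnia". Six further predictors go into separate exploratory models: "MSLT mean sleep latency, MSLT number of SOREMs, sex/gender, baseline ESS, age, and comorbidities". Then: "Significant predictors in univariate models will be combined in a multivariate model".

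The arms are small: "Sample size will be 22 in each group". The only response rate assumed anywhere is in the non-inferiority sample-size argument, where a responder is someone with a 25% reduction in ESS: "Assuming 80% of participants meet this threshold, 22 participants per group will provide 80% power".

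The plan does not say which response Aim 3 uses. The same section also calls participants responders on the PGI-C if they choose one of its two best improvement ratings, and it assumes no rate for that. It gives no sample-size reasoning for Aim 3, no expected split between narcolepsy type 2 and idiopathic hypersomnia, no method for sparse data or separation, and no predictor model for a continuous outcome. Continuous ESS change from baseline to week 12 is the primary outcome.

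**The concern.** In logistic regression the rarer outcome class limits what can be estimated. If most participants in an arm of 22 respond, a handful of non-responders must support the diagnosis model, six more single-predictor models and possibly a multivariable model. If either diagnosis group consists entirely of responders or entirely of non-responders, the log odds ratio for diagnosis has no finite estimate.

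Even where the model can be fitted, cutting ESS change at a threshold discards information that the trial already holds. Aim 3 is one of three stated aims, and the abstract says that all three are meant to inform the choice between the drugs. A finding of no predictor from a test with very low power could be misread as evidence that diagnosis does not matter.

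**Working it through.** **Inputs.** From the Statistical Analysis section: n = 22 per arm, SD of ESS change 6.2, and 80% response for a 25% ESS reduction. Assumed, because the documents do not give them: diagnosis splits of 11/11, 7/15 and 5/17 within an arm; true differences between diagnoses of 4 and 6 ESS points; normally distributed change; two-sided 5% tests.

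**The plan's own figure.** Non-inferiority with 80% response in both arms and a 30% margin, at one-sided 5% and 80% power: n = (1.645 + 0.842)² × 2 × 0.8 × 0.2 / 0.3² = 21.98, so 22 per group. The stated figure reproduces at that alpha. It concerns non-inferiority; the plan has no corresponding figure for Aim 3.

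**Step 1: non-responders at 80%.** 22 × 0.20 = 4.4 per arm. The binomial 95% range is 1 to 8, and the chance of 4 or fewer is 54%. With exactly 4 in an 11/11 split, even all 4 in one diagnosis gives Fisher p = 0.09.

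**Step 2: empty cells with no diagnosis effect.** For groups of k and m with response rate p, P(empty cell) = 1 − [1 − pᵏ − (1−p)ᵏ] × [1 − pᵐ − (1−p)ᵐ]. At p = 0.8:

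- 11/11: 1 − (1 − 0.0859)² = 16%
- 7/15: 1 − (1 − 0.2097)(1 − 0.0352) = 24%
- 5/17: 1 − (1 − 0.3280)(1 − 0.0225) = 34%

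At p = 0.55 the same formula gives 0.3%, 1.9% and 6.9%.

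**Step 3: empty cells with a diagnosis effect.** In an 11/11 split with overall response held at 80%, a 4-point difference corresponds to response rates of 88.7% and 71.3%, and 28% of arms have an empty cell. A 6-point difference corresponds to 92.3% and 67.7%, and the figure is 42%.

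**Step 4: power for diagnosis, 6 points, 11/11 split.** The binary tests are enumerated exactly over all 2×2 tables, with Wald counted as not significant when a cell is empty. The continuous test uses the noncentral t with 20 degrees of freedom and noncentrality 6 / (6.2 × √(2/11)) = 2.27.

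| Overall response | Wald | Fisher | Likelihood ratio | Continuous ESS change |
|---|---|---|---|---|
| 80% | 5% | 12% | 42% (true size 9%) | 58% |
| 65% | 28% | 23% | 45% | 58% |
| 55% | 39% | 26% | 45% | 58% |

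**Step 5: the continuous analysis at a smaller difference.** For 4 points the noncentrality is 4 / (6.2 × √(1/k + 1/m)):

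- 11/11: 1.51, power 30%
- 7/15: 1.41, power 27%
- 5/17: 1.27, power 23%

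At 80% response and 11/11, the binary tests of the same 4-point difference have 3% (Wald), 6% (Fisher) and 25% (likelihood ratio).

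Across response rates of 80%, 65% and 55%, differences of 4 to 8 points and all these splits in both directions, continuous ESS change had more power than each of the three binary tests.

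**The case against.** **The 80% rate may not apply to Aim 3.** This stands. The plan gives it for non-inferiority only and leaves Aim 3 response undefined, with PGI-C as a rival definition. Other figures in the plan suggest a lower rate. With a mean reduction of 4 to 5.3 points, SD 6.2 and an assumed baseline ESS of 14 to 18, a 25% reduction is 3.5 to 4.5 points, and about 47% to 61% would reach it under normality. Empty cells with no diagnosis effect are then uncommon. The loss of power remains.

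**The plan names no test, and the binary result depends on the test and the split.** This also stands. Likelihood-ratio power is far above Wald at 80% response, although part of the gain is inflated size. If the smaller diagnosis group responds worse (7/15, 6 points, 80% response), Wald reaches 18% and Fisher 22%; the continuous test has 52%.

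**The count of 4.4 may be too low.** Twenty-two is a completer target: "This study will recruit up to 55 participants, with a sample size target of 44 participants who complete participation". Analysis is by intention to treat with last observation carried forward, so early drop-outs may add non-responders. Even 55/2 = 27.5 per arm would give only 5.5 at 80% response, and some of the 55 may leave after a negative sleep study before receiving study drug.

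**ESS change does not replace PGI-C response.** Correct: PGI-C also covers sleep inertia and cognition, so PGI-C response should be kept as a supportive result.

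**The models are exploratory.** The plan uses that word for the other predictors; diagnosis is the main predictor of a stated aim.

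A reader might also infer that the significance screen would carry many chance findings into the multivariable model. At 80% response the Wald test for diagnosis rejects in only 0.7% to 1.9% of arms when there is no effect, so that does not follow for a Wald screen. The case against the multivariable step is that so few non-responders cannot support several predictors.

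**Conclusion.** The point holds as a cheap improvement to the Aim 3 analysis. Response needs a definition, and a linear model of ESS change is a better main analysis than logistic regression in arms of 22. It always gives a finite estimate for diagnosis when both diagnoses are present in the arm, and it has more power in every scenario examined.

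The size depends on the response rate. At 80%, empty cells affect 16% to 34% of arms with no diagnosis effect, and 28% or 42% (11/11) with a difference of 4 or 6 points. At 55% they affect 0.3% to 7% with no effect, and what remains is mainly lost power.

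A reader might conclude that Aim 3 as written is mostly inestimable or close to powerless. The documents do not support that in general: it requires the 80% rate to apply to Aim 3, which the plan does not say, together with a Wald or Fisher test and a balanced split or a worse response in the larger diagnosis group. Nor does the change make Aim 3 well powered, as the 23% to 30% at 4 points shows. Diagnosis splits, true differences and alpha are assumptions throughout. The primary comparison is not affected.

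**What to change.** In the Statistical Analysis section:

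1. Make the main Aim 3 analysis, within each medication, a linear regression of week-12 ESS change on diagnosis, adjusted for baseline ESS. Use the same model for each other exploratory predictor. Report estimates with confidence intervals.
2. For baseline ESS as a predictor in its own right, state that its association with change includes regression to the mean.
3. Define response for Aim 3. Report responder percentages by diagnosis, for the 25% ESS reduction and for PGI-C, as descriptive or supportive results. If they are modelled, use exact or penalised (Firth) logistic regression.
4. Drop the multivariable logistic model built from significant univariate predictors.

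The cost is one paragraph of wording, with no new data or participants. The downside is that the main results are in ESS points rather than odds of response, and PGI-C response is only supportive.
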